staining ECs will be rehydrated with PBS and nonspecific binding sites blocked with 5% donkey serum (Jackson Immunoresearch, West Grove, Pa). Afterward cells will be incubated with monoclonal antibodies for one of the following: nitrotyrosine (Abcam; Cambridge, Mass), xanthine oxidase (US Biological; Swampscott, Mass), NAD(P)H oxidase-p47phox (Abcam; Cambridge, Mass), CuZn SOD (Upstate; Lake Placid, NY), Mn SOD (Research Diagnostics; Concord, Mass), catalase (Abcam; Cambridge, Mass) or NF-KB p65 (Novus; Littleton, Colo). Cells will next be incubated with CY3-conjugated secondary antibodies (Research Diagnostics; Concord, Mass). For analysis, slides will be viewed using a fluorescence microscope (Eclipse 600, Nikon, Melville, NY) and EC images will be digitally captured by a Photometrics CoolSNAPfx digital camera (Roper Scientific, Inc., Tucson, Ariz). ECs will be documented by cell staining of von Willebrand factor and nuclear integrity will be confirmed using DAPI (4',6'-diamidino-2-phenylindole hydrochloride) staining. Once endothelial cells with intact nuclei are identified, they will be analyzed using Metamorph Software (Universal Imaging Corp, Downingtown, Pa) to quantify the intensity of CY3 staining (i.e. average pixel intensity). Values will be reported as ratios of EC protein expression/human umbilical vein EC (HUVEC); this minimizes the possible confounding effects of differences in intensity of staining among different staining sessions.

Exercise Testing: Passive leg movement will be performed by a member of the research team moving the participant's leg through a normal range of motion (90°- 180°).

Single contraction exercise protocols will be performed with either the upper (handgrip) or lower (knee extension) extremity. A single maximal voluntary contraction (MVC) will be established for each participant using a handgrip or knee extension dynamometer with an analog output. This MVC value will be used to calculate 10%, 20%, 30%, 40% and 50% of MVC for the single contraction. Following a 2 min baseline period the participant will perform the rapid (< 1 sec) single contraction and central and peripheral hemodynamics will be assessed for 1 min post contraction.

Active leg exercise will be performed using a custom-built knee-extensor ergometer with the participant moving the leg between 90°- 180° at a rate of approximately 60 rpm.

Plantar flexion exercises will be performed using an ergometer specifically designed to isolate the gastrocnemius and the soleus complex at a rate of approximately 60 rpm.

Handgrip exercise will be performed with the participant laying supine on the laboratory bed with handgrip dynamometer in their right hand. The right arm will be extended perpendicular to the participant's torso and supported by a height-adjustable table. Doppler ultrasound will be performed by a trained sonographer in order to obtain brachial artery blood flow measurements. Exercise will be performed for 4 stages each lasting 3 - 5 minutes and separated by at least 1 min of rest. Intensity will range from 10 to 60% of the participant's maximal handgrip strength. During exercise ECG and blood pressure will be continuously monitored. Arm exercise will involve rhythmic handgrip using a computer-interfaced dynamometer.

The graded exercise test will be performed on a cycle ergometer or treadmill using a conventional ramp test to exhaustion. Work rate/exercise intensity will be increased by an

appropriately tailored level from 2.5-25 watts in each step, depending upon capabilities. Pulmonary ventilation and gas exchange will be determined continuously using a low-resistance two-way breathing valve (Hans-Rudolph 2700, dead space 90 ml) and a pneumotachometer (Fleisch no. 3) on the expiratory side. Signals will be assimilated by a PC and O₂ and CO₂ analysis will be performed in real time (Parvo Medics, UT). All of this equipment is currently in place and has been used routinely in our laboratory with both healthy volunteers and patients. Throughout all our exercise testing, safety is ensured through careful echocardiogram (ECG) monitoring, availability of a defibrillator, an oxygen source, emergency drugs, and attendance of qualified personnel.

Flow Mediated Dilation (FMD): After 15-20 minutes in the supine position a blood pressure cuff will be placed on the lower leg or forearm. Ultrasound images of the artery and Doppler waveforms will be obtained prior to cuff inflation (baseline). The cuff will then be inflated to 250mmHg for 5 minutes. Following the cuff release, ultrasound images of the popliteal artery and Doppler waveforms will be recorded continuously for 2 minutes. During this time, arterial images during diastole will be captured by image analysis software (Medical Imaging Applications). All recorded ultrasound images and velocity spectra segments will be saved to the GE Logiq 7 hard drive for off-line image and waveform analysis. The time averaged, and intensity-weighted mean blood velocity (Vmean) will be averaged across 5 second intervals for the entire 2 minute clip following cuff release. In addition, edge detecting software will be utilized to measure arterial diameter frame by frame, which will also be averaged into 5 second intervals. Summed shear rate throughout the 2 minutes will be calculated based on vessel diameter and blood velocity. The maximum change in vessel diameter, relative to baseline, will be determined and expressed as %FMD and %FMD/summed shear rate. A greater FMD response is an indicator of healthier vessels. A typical response for a young healthy participants would be 8 - 12% or greater dilation, whereas a poor response would be <5%. In addition, it is also important to be able to express the change in diameter relative to shear stress, as the shear stress is the stimulus for the NO-induced dilation. Again, greater FMD/shear values are indicative of healthier vessels.

Limb blood flow: Blood flow will be measured with an ultrasound Doppler (Logiq 7, GE) equipped with linear array mechanical sector transducers operating at an imaging frequency of 10-14 MHz. Vessel diameter will be determined at a perpendicular angle along the central axis of the scanned area, where the best spatial resolution can be achieved. The blood velocity profile will be obtained using the same transducers with Doppler frequency of 4.0-5.0 MHz, operated at high-pulsed repetition frequency mode (2-25 kHz) with a depth of 1.5-3.5cm. Special care will be taken to avoid aliasing, to ensure that probe position is stable, the insonation angle does not vary, and that the sample volume is positioned in the center of the vessel and adjusted to cover the width of the diameter and the blood velocity distribution. Blood velocity measurements will be obtained with the probe at an appropriate angle to maintain an insonation angle of 60° or less and the sample volume centered. Using arterial diameter and mean velocity (Vmean), blood flow will be calculated as: *Blood Flow (mL/min) = Vmean · π · (Vessel Diameter/2)² · 60.*

Statistical Methods, Data Analysis and Interpretation

A total of 72 participants will be recruited for the protocols outlined above. While participation in more than one study will not be compulsory, we will invite all participants to participate in multiple protocols to strengthen the statistical comparisons. The data will be collected in a series of integrated protocols performed at different visits for each specific aim. Power analysis (discussed in detail below) based on preliminary work in our laboratory and previous findings in the literature reveals that 20 participants per group will result in adequate power to determine significant differences between hypertensive and normotensive participants for each of the specific aims. At each of the visits involving catheterization, the femoral artery and vein in the exercising limb will be catheterized allowing continuous blood pressure measurement, repeated measures of arterial blood flow, and arterial-venous metabolite determinants (such as O₂ and free radical concentrations to measure delivery or production rates). Measurements will be made at specific time points before, during and after knee extension exercise. The exercise stages of the protocol include baseline (stage 0), passive movement (stage 1), and 3 exercise levels (25% = stage 2, 50% = stage 3, and 75% = stage 4 of previously determined maximum single-leg work load). A key variable to be measured will be the exercise pressor reflex (EPR), which for the purpose of data analysis is strictly defined as the steady state blood pressure at a given stage of exercise minus the baseline (stage 0) blood pressure. Analogous responses will be calculated for changes in blood flow and oxygen delivery. Measurements during passive movement (stage 1) and PECO are used to address separate hypotheses regarding the contribution of mechanoreceptor and metaboreceptor afferent feedback. The approach for analysis of EPR is given below, comparable statistical methods will be applied to the other variables and are not discussed in detail here.

The magnitude of the EPR is expected to be influenced by afferent feedback (Specific Aim #1), sympathetic activity (Specific Aim #2), and oxidative stress (Specific Aim #3). The main hypothesis of each specific aim posits that the tested component will be greater in hypertensive than normotensive participants. The outcome variable to be compared is the difference in EPR before and after a given treatment. Thus, if uEPR₄ is the untreated EPR at stage 4 and fEPR₄ is the EPR measured after fentanyl administration, then (uEPR₄ - fEPR₄) may be considered the afferent-mediated portion of the EPR and is compared in hypertensive versus normotensive. Since untreated and fentanyl-treated EPRs will be generated at 3 graded exercise levels, a repeated measures ANCOVA using a mixed general linear model (with participant as the repeated measure) will be tested with the dependent variable as (uEPR_i - fEPR_i) (where i = 2 to 4 for the respective exercise stages) and independent variables will include age, gender, hypertension status, and i (exercise stage).

Power analyses are summarized in the tables below. The strategy for these analyses was to conservatively test power for outcomes at stage 4 (e.g., uEPR₄ - fEPR₄), comparing hypertensive to normotensive, recognizing that the inclusion of the supporting measures at exercise stages 2 and 3 will only serve to increase power.

Clinical Records: Patient demographics (DOB, gender, height, weight), past medical history, medication use, and results of cardiovascular tests (echocardiogram, catheterization, stress test) will be collected

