applied topically prior to exercise. Each exercise intensity may be continued for up to 5 min to achieve steady-state pulmonary oxygen consumption. During each work bout the following sequence of events may be conducted (as indicated by the arrows in the timeline below): (1) sampling of femoral arterial and venous blood for the direct measurement of free radicals and blood gases, (2) continuous measurement of central hemodynamics (heart rate, stroke volume, cardiac output) and arterial and venous pressures (indwelling catheter pressure), and (3) leg or arm blood flow via ultrasound Doppler. Immediately following each exercise stage PECO may be performed. After a 90 min recovery, the protocol may be repeated in the fentanyl/afferent blocked condition. The efficacy and extent of the block may be tested by neurological exam including cutaneous hypoesthesia to pinprick and cold perception on the torso, upper, and lower limbs.

PROTOCOL 2: Determine the contribution of sympathetically-mediated vasoconstriction to the exercise pressor reflex and blood flow response in hypertension. (1 day, 6 - 8 hours)

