Participants will report to the laboratory (VA bldg. 2 room 1D21) in a fasted state. Catheters may be placed in the leg (common femoral artery and femoral vein) or arm (brachial artery and antecubital vein) by a licensed physician using standard sterile technique. During the catheterization process endothelial cells may be collected using the sterile J-wire (see **Participant Instrumentation** for more detailed description of this procedure). It should be noted that the insertion of the J-wire is common practice for catheter placement. Following placement of catheters, resting measurements of arterial blood pressure, heart rate, and limb blood flow (ultrasound Doppler) may be taken, and resting blood samples (arterial and venous) may be collected. Phenylephrine (PE, α 1 selective) and dexmedetomidine (DEX, α 2-selective) dose-responses may be performed at rest to establish maximal α -adrenergic mediated vasoconstriction (Timeline A). Dose responses may consist of up to 7 doubling doses of PE and DEX starting at approximately 0.05 mcg/dl/min and 1.5 ng/dl/min, respectively. Each dose may be infused for 1 to 5 min. Following ~30 min of drug washout and the return of basal blood flow KE, plantar flexion, or handgrip exercise may be performed with PE or DEX infusion. Several bouts of exercise may be performed at exercise intensities including, but not limited to, 25, 50, and 75% of WR_{max}. Each exercise intensity may be continued for up to 10. During each work bout the following sequence of events may be conducted: pre-infusion (control) recording of blood flow and central hemodynamics; pre-infusion (control) sampling of arterial and venous blood for measurement of blood gases and norepinephrine; and infusion of PE or DEX with continuous monitoring of blood flow and central hemodynamics. The order of the PE or DEX trials may be counterbalanced and infusion rates will be matched and adjusted to account for increases in blood flow during exercise²¹. After ~60 min of recovery and the return of basal blood flow and central hemodynamics, phentolamine (PHEN, non-selective α -adrenergic antagonist) may be infused at rest at three doses (5, 10, and 20 mcg/dl/min) followed by a norepinephrine (NE) challenge (~20 ng/dl/min) to test the efficacy of the phentolamine-induced inhibition of α -adrenergic vasoconstriction (Timeline B). Immediately following the NE challenge exercise may commence with continuous PHEN infusion. Several exercise bouts including, but not limited to, 25, 50, and 75% of WR_{max} may be performed. Each exercise bout may be performed for up to 6 min and periods of recovery

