
may be included between exercise bouts. Identical measures as previously described for the pre-infusion portion of the agonist trials may be repeated.

Prior to reporting to the laboratory participants may undergo an acute (1 dose) dietary supplementation by consuming two nitrate rich beetroot juice (70 ml per drink, 13 mM/day, 0.9g of nitrates) or nitrate-depleted placebos (70 ml per drink, 0mM/day, 0.0g of nitrates). Participants will be instructed to drink two 70 ml containers of placebo on the day of the experiment approximately 1 to 2 hours before the start of the study. Following the first half of the trial (corresponding to the "A" timeline below), the participant will drink two 70ml nitrate rich beetroot juice supplements and repeat the series of exercise bouts 2 hours following consumption. During this supplementation period participants will be asked to refrain eating abnormal amounts (>300g/day) of leafy green vegetables (e.g. spinach), consumption of alcohol, and the use of mouthwash products containing alcohol.

To determine whether the amendment for dietary nitrate requires an IND we have been following the guidelines put forth by the FDA in the document entitled: **Guidance for Clinical Investigators, Sponsors, and IRBs: Investigational New Drug Applications (INDs) - Determining Whether Human Research Studies Can Be Conducted Without an IND** - page 15 of the document states the following "If the clinical investigation is intended only to evaluate the dietary supplement's effect on the structure or function of the body, an IND is not required. Our investigation is not intended to mitigate, cure, treat, or prevent a disease. Based on these guidelines the dietary supplement proposed is 1) not considered a drug, 2) will not be used to diagnose, cure, mitigate, treat, or prevent a disease, and 3) will be used to characterize the mechanism by which the supplement acts to maintain structure or function (specifically, blood flow). Therefore, based on these guidelines, as explicitly stated by the FDA, we believe an IND is not required.

PROTOCOL 3: Determine how endothelial-dependent and endothelial independent mechanisms contribute to impaired vascular function in hypertension. (1 day, 5 - 7 hours).

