Participants will report to the laboratory (VA bldg. 2 room 1D21) at ~ 0800 in a fasted state, having abstained from caffeine and exercise for the past 12 hours. Catheters may be placed in the leg (common femoral artery and femoral vein) or arm (brachial artery and antecubital vein) by a licensed physician using standard sterile technique. During the catheterization process endothelial cells may be collected using the sterile J-wire (see Participants Instrumentation for more detailed description of this procedure). It should be noted that the insertion of the J-wire is common practice for catheter placement. Following placement of catheters, resting measurements of arterial blood pressure, heart rate, and limb blood flow (ultrasound Doppler) will be taken, and resting blood samples (arterial and venous) may be collected. Control measures may be made at rest, during passive limb movement, exercise, and immediately following exercise during post exercise circulatory occlusion (PECO). Protocol 4 is nearly identical to protocol 1 with the potential addition of flow mediated dilation (FMD) to assess vascular function in the popliteal, femoral or brachial artery. The FMD will be performed in accordance with recently published guidelines ²² employing distal cuff placement for 5 min at 250 mmHg and continuous assessment of arterial diameter for 2 min following cuff release using edge detection software. All measures will first be performed in the control condition. During each work bout the following sequence of events may be conducted (as indicated by the arrows in the timeline below): (1) sampling of arterial and venous blood for the direct measurement of free radicals, blood gases, and markers of oxidative stress (ascorbic acid, glutathione, lipid hydroperoxide, 8-isoprostanes, nitrite/nitrate, ferric reducing ability of plasma). (2) continuous measurement of central hemodynamics (heart rate, stroke volume, cardiac output) and arterial and venous pressures, and (3) femoral blood flow via ultrasound Doppler. After a 120 min recovery, the protocol may be repeated following administration of an oral antioxidant cocktail (AOC, consisting of 1000 mg vitamin C, 600 IU vitamin E, and 600 mg alpha lipoic acid) or infusion of vitamin C (range 1 to 5 grams). We have previously reported reduced oxidative stress, diminished free radical levels, and improved vascular function with this AOC ²³⁻²⁷. Moreover, this 120 min period is of sufficient duration to allow for vitamin absorption into the circulation. Endothelial cells (if collected using the J-wire technique during catheterization for Specific Aims 1, 2, and 3), may be measured for nitrotyrosine, NAD(P)H oxidase, xanthine oxidase, superoxide dismutase, catalase, nuclear factor-KB (NF-KB).

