Central hemodynamics: Heart rate, stroke volume, cardiac output, and mean arterial pressure will be determined non-invasively with a finometer (Finapres Medical Systems, Amsterdam, The Netherlands) positioned at heart level. The finometer uses beat by beat arterial pressure waveform analysis as assessed by photoplethysmography using the Modelflow method (Beatscope, version 1.1; Finapres Medical Systems), which in combination with heart rate has been documented to accurately estimate cardiac output during a variety of experimental protocols^{46,47}. This technique requires a blood pressure cuff be placed on the upper arm (biceps) and on the finger of the participant. Mean arterial blood pressure will also be measured by an automatic sphygmometer (Tango+, Suntech, North Carolina) at rest and during exercise.

Dietary Nitrate Supplementation: Nitrate-rich (70 ml per drink, 5 mM/day, 0.45g of nitrates) or nitrate-depleted (placebo; 70 ml per drink, 0mM/day, 0.0g of nitrates) beetroot juice will be consumed for 1 to 5 consecutive days prior to reporting to laboratory. This supplement is commercially available (Beet It, James White Drinks, Ipswich, UK) and has been reported to reduce blood pressure and improve exercise performance by increasing nitric oxide bioavailability⁴⁸⁻⁵³.

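### In the optional same-day nitrate schedule placebo always precedes nitrate with no time control in the text, so the placebo-to-nitrate change in exercise blood flow cannot be separated from time

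*Combined protocol and SAP*

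**What the plan says.** All references are to the combined protocol and SAP.

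**Nitrate (Study Procedures, Protocol 2).** Supplementation is optional: "participants may undergo an acute (1 dose) dietary supplementation by consuming two nitrate rich beetroot juice", or a nitrate-depleted placebo. The text then fixes one order. Before the first run: "Participants will be instructed to drink two 70 ml containers of placebo on the day of the experiment". After the first half: "the participant will drink two 70ml nitrate rich beetroot juice supplements and repeat the series of exercise bouts 2 hours following consumption". No other order is given for this schedule, and no time control.

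**Nitrate (Participant Instrumentation, Dietary Nitrate Supplementation).** Here "beetroot juice will be consumed for 1 to 5 consecutive days prior to reporting to laboratory", with no allocation or order stated.

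**Other treated runs.**
- Protocol 1: "After a 90 min recovery, the protocol may be repeated in the fentanyl/afferent blocked condition".
- Protocol 2: "After ~60 min of recovery and the return of basal blood flow and central hemodynamics, phentolamine" may be infused, after the agonist trials.
- Protocol 4: "All measures will first be performed in the control condition", and then "After a 120 min recovery, the protocol may be repeated following administration of an oral antioxidant cocktail". A vitamin C infusion is an alternative.
- Protocol 5a: the control run comes first, then the cocktail and a two-hour rest. Vitamin C infused before or during exercise is an alternative. An optional time control in an unsized subset is mentioned. It is the only time control in the text.

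**Aims and analysis.** The Protocol 2 aim predicts that nitrate raises blood flow by helping the body oppose α-adrenergic vasoconstriction during exercise. The Statistical Methods take the before-to-after change in the exercise pressor reflex (EPR) as outcome and compare it between hypertensive and normotensive participants. The model contains age, gender, hypertension status and exercise stage.

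**The concern.** If every participant has the treated run second, on the same day and after earlier exercise and infusions, the change between runs contains both the treatment effect and whatever changes with time: fatigue, recovery, residual drug or instrument drift. The aims are worded as treatment effects, and for nitrate on the same-day schedule the only comparison is within person. The authors recognise the risk, since the Protocol 5a time control is there to guard against it, but they leave it optional, unsized and confined to that protocol. At stake is whether a change in blood flow after nitrate may be reported as an effect of nitrate, and what the group contrast for the other treatments assumes.

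**Working it through.** **1. The plan's own figure.** The Statistical Methods give 20 per group. The available text states no significance level, effect size or SD, and the power tables it announces are not in it, so the figure cannot be reproduced. For reference, assuming two-sided 5% and 80% power with the normal approximation, 20 per group corresponds to (1.960 + 0.842) × √(2/20) = 0.886 SD. Nothing below depends on this.

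**2. What the within-person change estimates.** Let τ be the treatment effect and π the change that would occur between runs without treatment. With one order only,

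E(second run − first run) = τ + π.

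The pairs (τ = a, π = 0) and (τ = 0, π = a) give identical data. The planned model has no period term, but adding one would not help: period and treatment coincide. Only a second order or a time control separates them.

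**3. The control within each bout.** Protocol 2 records flow before infusion in each bout and then during phenylephrine or dexmedetomidine. For the vasoconstrictor response (infusion minus pre-infusion flow), a shift in flow level that is the same in both readings cancels. Two things do not cancel between runs: a change in pre-infusion exercise flow, which is itself the quantity expected to rise with nitrate, and a change in responsiveness to the agonist.

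**4. Baseline subtraction.** The EPR is the stage value minus stage 0, which removes drift in resting level if stage 0 is re-measured in each run. For fentanyl and the antioxidant, the natural reading is that it is: the protocol is repeated, and the fentanyl EPR is defined as measured after administration. For nitrate only the exercise bouts are said to be repeated, so this is unclear. Drift in the response to exercise remains in either case. The return to basal values before phentolamine also covers rest only.

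**5. The planned group contrast.** With H hypertensive and N normotensive,

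E(change in H − change in N) = (τ_H − τ_N) + (π_H − π_N).

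Common drift gives π_H − π_N = 0. Differing drift stays in.

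**6. Illustrative size.** No drift size is given, so δ is assumed, in SDs of the within-person change, with no true effect and two-sided 5%. The false-positive rate is P(|T| > t₀.₉₇₅), T noncentral t. Two groups of n: noncentrality δ√(n/2), df 2n − 2. One group: δ√n, df n − 1. Example, 20 v 20 and δ = 0.5: 0.5 × √10 = 1.581, df 38, rate 0.338.

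| | δ = 0.1 | 0.25 | 0.5 | 0.75 |
|---|---|---|---|---|
| Group contrast, common drift δ | 5% | 5% | 5% | 5% |
| Group contrast, drift differs by δ, 20 v 20 | 6% | 12% | 34% | 64% |
| Same, 10 v 10 | 6% | 8% | 19% | 36% |
| One-group within-person test, n = 20 | 7% | 19% | 56% | 89% |
| Same, n = 10 | 6% | 11% | 29% | 56% |

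Simulation (20,000 trials, 20 v 20) gave 5.3% with common drift of 0.5 and 33.7% with drift differing by 0.5. The 20 per group is stated for each aim, not for the optional nitrate part, so 10 is shown as well. The SAP does not specify the one-group test in the last two rows.

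**The case against.** The strongest reply is that the plan's inference is the hypertensive-versus-normotensive contrast, with comparable methods for the other variables, and that this contrast stays at 5% under common drift. That stands. A reader might infer from the one-group rows that the trial's error rate is 56% or 89%. The documents do not support this: no one-group test is planned, and the drift sizes are assumed. Nor do they give evidence that drift differs between groups.

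Other replies, and what stands:

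- *The nitrate aim concerns vasoconstriction, and each bout has its own pre-infusion control.* Correct for drift in flow level within the vasoconstrictor response, but not for pre-infusion flow or agonist responsiveness.
- *Stage 0 belongs to the repeated protocol.* This stands for fentanyl and the antioxidant. It would be wrong to say that their baseline is not repeated.
- *The trial is labelled placebo controlled, and an antioxidant placebo is mentioned.* On the same-day nitrate schedule placebo is always first. For the antioxidant, the text does not say who takes placebo or in which run.
- *A control may be drawn in a timeline figure.* This cannot be excluded, so the point is limited to the text.
- *Control first is sensible, because nitrate could carry over into a later placebo run.* A fair reason, and why a randomised same-day order is not demanded here.
- *Protocol 5a may include normotensive participants.* The Objectives cover healthy and hypertensive people, and the sample size is given per group for each aim. A reader might infer that 5a has no group contrast; the text does not settle it.

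**Conclusion.** The point holds for the same-day nitrate schedule. The placebo-to-nitrate change in exercise blood flow is confounded with time, and that comparison alone cannot support the statement that nitrate improves flow. This follows from the stated order and needs no assumption about size, apart from the possibility of a control shown only in the missing figures.

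For fentanyl, phentolamine and the repeat-run antioxidant the point is narrower. The planned group contrast is sound if drift is equal in both groups, an assumption the plan does not state. If drift differs by an assumed 0.1 SD, the error is close to nominal (6%); at 0.5 SD it is 34% with 20 v 20. The true value is unknown.

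The differing nitrate descriptions are a separate documentation problem and not evidence of confounding. Protocol 2 has one dose, 13 mM/day and 0.9 g; Participant Instrumentation has 1 to 5 days, 5 mM/day and 0.45 g. The gram figures agree if 0.45 g is per drink (2 × 0.45 = 0.9), and one day lies within 1 to 5. The mM/day figures do not agree even if doubled (2 × 5 = 10 against 13).

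This should be fixed, mainly in text. Confidence is moderate.

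**What to change.** 1. Add to the Statistical Methods: *Where the treated run always follows the control run on the same day, the change between runs is not controlled for time and will not by itself be attributed to the treatment unless it is compared with a concurrent time control; the hypertensive-versus-normotensive contrast of that change assumes equal drift in both groups.* Keep the hypotheses in the specific aims as they are, and report uncontrolled within-person changes as descriptive.
2. In Protocol 5a, replace the optional, unsized time control with a stated number of participants who will perform it, and compare the antioxidant change with the time-control change. If these are separate participants, a small number gives little precision: in SD units the standard error is √(1/30 + 1/10) = 0.365 with 30 treated v 10 controls and √(1/20 + 1/20) = 0.316 with 20 v 20. Power for an assumed 0.5 SD effect is then 27% and 34%. The number should be chosen with this in view.
3. State that stage 0 is re-measured before the repeated nitrate bouts.
4. Separately, reconcile the two nitrate descriptions so that timing and content are stated once. No view is taken on which is right.

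**Cost.** Text, at most one extra resting reading before the nitrate bouts, and some Protocol 5a participants doing the time control. Uncontrolled within-person changes can no longer be claimed as treatment effects.

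**Not required.** Randomising the same-day order risks nitrate carryover. Giving some participants placebo before the second run reduces the number treated: at an assumed 0.91 SD, power of the group contrast falls from 80% (20 v 20) to 67% (15 v 15) or 49% (10 v 10). Both are trade-offs for the sponsor.
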